6.2 PREPARATION/HANDLING/STORAGE/ACCOUNTABILITY

6.2.1 ACQUISITION AND ACCOUNTABILITY

Inventory of the BTG-001933 product will be maintained by the study team in a secure location with dispensing records completed to document supply receipt, dispensation, and return of unused product.

6.2.2 FORMULATION, APPEARANCE, PACKAGING, AND LABELING

The BTG-001933 product is provided by the manufacturer (Biocompatibles UK, Ltd) packaged as individual cartons containing one vial of product and one ViaLok Vented Vial Access Device (Yukon Medical LLC). The vial and carton are labeled For Investigational Use Only.

The primary packaging material of the vial includes:

| Material | Description |
|-----------------------------|--|
| 10 ml glass vial | 10ml ISO Clear Type I Glass Vial with 20mm Crimp Neck |
| Vial stopper | 20 mm fluoropolymer film coated bromobutyl rubber Injection stopper 4023/50 Grey B2-40 Westar® RS |
| Flip-off tear-off crimp cap | Aluminum cap with a colored plastic (polypropylene) button seal Size 100 – 200µm: red |

6.2.3 PRODUCT STORAGE AND STABILITY

Based on the evidence of 24 months shelf life for LC Bead LUMI™ and available 6 months real time and accelerated stability data for BTG-001933, an initial shelf life claim for the investigational device BTG-001933 for use in clinical studies of 18 months at 2 – 25°C has been defined. The shelf life will be extended based on the results of ongoing stability studies, if appropriate.

The following storage conditions are defined for BTG-001933:

- Unopened BTG-001933 must be stored between 2°C to 25°C, in a dry place in its original packaging. Protect the product from light.
- Use by the date indicated on the vial label.
- Do not freeze.

6.2.4 PREPARATION

The bead suspension of BTG-001933 in buffered saline is to be transferred from the vial into a 10 mL syringe by using the transfer device prior to administration to the patient. The transfer device is supplied with the product and is co-packaged in the device carton with the BTG-001933 vial. The transfer device (20 mm ViaLok Vented Vial Access Device (Yukon Medical LLC)) is a sterile medical device intended to access standard vials for needle-free preparation and administration. Details of product preparation are given in the manufacturer's Instruction for Use.

6.3 MEASURES TO MINIMIZE BIAS: SITE TRAINING RANDOMIZATION AND BLINDING

Of the 59 participants who will participate in this research, 27 participants will be randomized to the intervention arm, and 27 participants will be randomized to the control arm. The first 10 patients to meet all eligibility criteria will be the 10 pilot patients; these patients will not be analyzed with the randomized patients.

In this double-blind experiment, neither blinded study team nor participants will know the details of the participants' randomization. Unblinded members of the study team will perform the procedure and have access to the medical record in case of emergency. All study visits involving study intervention and the details of the procedure, including start/stop times, will be recorded on the relevant eCRF by the unblinded team member.

All participants will undergo the same preparation for the procedure, then, when the procedure begins, the participants will be blindfolded with a head drape and will have their hearing damped with ear plugs and noise-cancelling headphones, preventing them from seeing and hearing the procedure, but still allowing them to keep in contact with the procedure team. All procedure images and reports, regardless of the randomization arm, will be kept with the unblinded member of the study team, and will not be housed centrally. All participants will adhere to the same follow-up schedule, meeting with blinded members of the study team only. The procedural team will not have further contact with the participant, the participant will only be followed by the blinded study team.

After all subjects complete the follow-up period, the study team and the subjects will each complete a survey to determine to which arm they thought each subject was randomized. After the surveys are completed, both the investigator and subject will be unblinded at the same time. Once the study is closed all reports and images will be entered into the clinical record.

6.4 STUDY INTERVENTION COMPLIANCE

Embolization and device placement will be assessed by radiographic imaging.

Subject-completed logs recording diet, hunger levels, weight, and symptoms will be reviewed to determine compliance with the weight management intervention prior to the procedure and during the follow-up period.

6.5 CONCOMITANT THERAPY

The participant will be asked to take an oral proton pump inhibitor (Omeprazole 40 mg, daily) and an oral cytoprotective agent (Sucralfate 1 g, two times a day), which coats and protects the stomach lining for two weeks before and six weeks after the procedure to prevent stomach irritation. Participants suffering from diabetes will be asked to withhold their diabetes medication on the day of the procedure.

Daily NSAID use should be avoided to reduce the risk for peptic ulcer disease.

At every study visit, new medications or changes in concurrent medications on the appropriate concurrent medication eCRF will be recorded. Documentation will include dosage, start/stop dates and any drug holidays.

For this protocol, a prescription medication is defined as a medication that can be prescribed only by a properly authorized/licensed clinician. Medications to be reported in the Case Report Form (CRF) are concomitant prescription medications, over-the-counter medications and supplements.

7 STUDY INTERVENTION DISCONTINUATION AND PARTICIPANT DISCONTINUATION/WITHDRAWAL

7.1 DISCONTINUATION OF STUDY INTERVENTION

All decisions to stop the study in any subject, or the study as a whole, will be made by the DSMB, a multidisciplinary team. This team will include a gastroenterologist, psychologists, obesity specialist, bariatric surgeon, and interventional radiologists. If the DSMB decides to remove a subject, the investigator will refer the subject to necessary medical care for follow-up.

The DSMB will halt the study for evaluation and possible discontinuation if one or more subjects experience any of the following events:

- Gastric ulcerations which require endoscopic or surgical intervention
- Gastrointestinal bleeding that reduces hemoglobin >3 gm/dL
- Significant abdominal pain requiring hospitalization >48 hours post procedure
- Inability to retain ingested fluid or solid food >48 hours post procedure due to persistent nausea and vomiting
- Radiation overexposures
- Any other unexpected organ injury that could be related to the procedure including but not limited to the following: abdominal abscess, bowel infarction or perforation, hypoxemia, azotemia, heart failure, pulmonary venous congestion, shock, deep vein thrombosis, pulmonary emboli or death

Discontinuation from study intervention does not mean discontinuation from the study, and remaining study procedures should be completed as indicated by the study protocol. If a clinically significant finding is identified (including, but not limited to changes from baseline) after enrollment, the investigator or qualified designee will determine if any change in participant management is needed. Any new clinically relevant finding will be reported as an adverse event (AE).

The data to be collected at the time of study intervention discontinuation will include the following:

- For subjects who withdraw before the end of the study, all End of Study assessments should be completed, if possible, prior to withdrawal. All AEs must be documented in the patient medical notes and in the electronic case report form (eCRF).
- If a subject withdraws from the study for any reason, all efforts should be made to follow AEs unless the subject withdraws consent.

7.2 PARTICIPANT DISCONTINUATION/WITHDRAWAL FROM THE STUDY

Subjects are free to withdraw from participation in the study at any time upon request.

The DSMB will determine if stopping rules apply. Stopping rules that would necessitate withdrawal of any individual subject include development of any of the following conditions during the six-month period following the procedure. All efforts should be made to follow AEs to resolution or stabilization unless the subject withdraws consent:

- Development of gastric ulceration observed at the follow-up endoscopy that requires surgical therapy. If ulceration can be managed medically, it will be treated by a gastroenterologist, and the participant will remain in the study.
- Small bowel obstruction, hernia, small bowel incarceration, abdominal abscess, gastrointestinal bleed, hypotension, new onset cardiac ectopy, bradycardia, tachycardia, bowel perforation, pneumothorax, pneumonia, hypoxemia, azotemia, heart failure, CO₂ narcosis, ventricular bigeminy, pulmonary venous congestion, septicemia, shock, mesenteric venous thrombosis, deep vein thrombosis, pulmonary emboli, adhesions, or death.
- Subjects may also be removed from the study by the investigator for the following reasons:
 - Staying in the study would be harmful to the subject (this includes new pregnancy during follow-up).
 - The subject needs treatment that is not allowed in the study.
 - It is decided that another therapeutic approach can improve the subject's medical care.
 - The subject fails to follow instructions.
 - The subject is not complying with study visits.
 - The study is cancelled.
 - There may be other reasons to remove study subjects that are not known at this time.

The reason for participant discontinuation or withdrawal from the study will be recorded on the electronic Case Report Form (eCRF). Subjects who sign the informed consent form and are randomized but do not receive the study intervention may be replaced. Subjects who sign the informed consent form, and are randomized and receive the study intervention, and subsequently withdraw, or are withdrawn or discontinued from the study will not be replaced.

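### Protocol 7.2 takes treated participants out of the study, and nothing then obtains their month-12 weight; capture of later adverse events is unclear

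*Protocol*

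**What the plan says.** Protocol 7.2 provides two routes out of the study for a participant who has already been treated.

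- **Listed conditions.** "Stopping rules that would necessitate withdrawal of any individual subject include development of any of the following conditions during the six-month period" after the procedure. The list runs from surgically treated ulcer, gastrointestinal bleed, perforation and mesenteric venous thrombosis to hernia, hypotension, tachycardia and pneumonia. Ulcers that can be managed medically do not lead to removal. The decision sits with the board: "The DSMB will determine if stopping rules apply".
- **Investigator discretion.** Reasons include "The subject is not complying with study visits" and "It is decided that another therapeutic approach can improve" the participant's care.

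Treated participants who leave are not replaced. On data after removal, Protocol 7.1 says "all End of Study assessments should be completed, if possible, prior to withdrawal", and "If the DSMB decides to remove a subject, the investigator will refer the subject to necessary medical care for follow-up". On adverse events, 7.1 says "If a subject withdraws from the study for any reason, all efforts should be made to follow AEs unless the subject withdraws consent", while 7.2 says "All efforts should be made to follow AEs to resolution or stabilization unless the subject withdraws consent". Protocol 8.3.3 ends adverse-event collection on the participant's last day in the study. The primary efficacy endpoint is weight change at 12 months, and the primary safety endpoint counts adverse events over the same 12 months (Protocol 1.1, SAP 3.5).

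**The concern.** An intention-to-treat comparison needs the month-12 weight of everyone randomised, whatever happened after the procedure. Section 7.2 ends participation in a way that may depend on arm (embolization complications) or on the weight course (non-compliance, or another therapy judged better). The missing endpoints are then informative, and the trial has created some of them itself, in people who could often still be weighed.

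The bias could go either way. Complication removals may fall more on BAE; discretionary removals may fall as much or more on sham; and a gastrointestinal complication could go with more weight loss rather than less.

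The analysis does not repair this. SAP 6.0 imputes missing month-12 weights within arm from participants who have one, using age, race, sex and baseline weight. Neither the exit weight nor the reason for removal enters the model, so a removed participant is imputed as a typical completer.

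**Working it through.** **Does any text obtain the month-12 weight?**

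- 7.1 states that stopping the intervention is not the same as leaving the study and that remaining procedures go on. It does not clearly reach someone withdrawn from the study under 7.2.
- The End of Study assessment in 7.1 comes before withdrawal, so it gives a weight at exit, not at month 12.
- 7.3 covers recontact after missed visits and loss to follow-up, not people the study removes.
- Weights from weight-management visits (8.2.3) stop at exit.
- Withdrawal reasons are recorded on the eCRF and dropout reasons appear in the CONSORT diagram (SAP 2.0), but a reason is not a weight.

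**Adverse events.** 7.1 is broad: follow-up after withdrawal for any reason, not limited to the triggering event. 7.2 (until resolved or stable) and 8.3.3 (last day of participation) can be read as leaving out an event that starts after removal but before month 12.

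**The plan's own figure.** Inputs from Protocol 9.2: losses of 8 and 3.3 kg (difference 4.7 kg), SD 7 kg, two-sided alpha 0.20.

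- Standard error at 21 per arm = 7 × √(2/21) = 2.160 kg.
- Power of the two-sample t-test (noncentral t): 0.794 at 20 per arm and 0.809 at 21, so 21 is the smallest number reaching 80%.
- 21 / (1 − 0.20) = 26.25, rounded up to 27. The stated figures reproduce.

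**Size of the bias, with assumed inputs.** The documents give neither a removal rate nor a weight gap. Suppose k1 and k2 participants are removed from the two arms of 27, and each differs from same-arm completers by a gap g (same size and sign in both arms). Treating them as typical completers shifts the arm difference by

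shift = (k1 − k2)/27 × g.

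For 3 v 1 removed, with 21 weights per arm and the other missing weights non-informative:

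| Gap | Shift | Share of 4.7 kg | Rejection under no effect | Power, toward null | Power, away |
|---|---|---|---|---|---|
| none | 0 | 0% | 0.200 | 0.809 | 0.809 |
| 3 kg | 0.222 kg | 4.7% | 0.202 | 0.780 | 0.835 |
| 5 kg | 0.370 kg | 7.9% | 0.206 | 0.759 | 0.851 |
| 8 kg | 0.593 kg | 12.6% | 0.216 | 0.727 | 0.874 |

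If only those four weights are missing (24 v 26 observed) and the gap is 5 kg, rejection under no effect is 0.208, and power moves from 0.858 to 0.812 or 0.895. Equal removals with equal gaps (3 v 3) give a shift of 0. A more extreme case, 3 to 5 removed from BAE, none from sham, and an 8 kg gap, gives shifts of 0.89 to 1.48 kg and rejection under no effect of 0.24 to 0.30.

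**Are such counts plausible?** Protocol 2.2.4 reports no major adverse event in 20 pilot participants. The exact one-sided 95% upper bound is 1 − 0.05^(1/20) = 0.139, and 0.139 × 27 = 3.8 participants. That pilot used larger beads (300–500 µm), and a major adverse event is not the same thing as the 7.2 list.

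**The case against.** **The dismissal of 7.1 is disputable.** Protocol 6.4 treats weight management as part of the intervention, and that programme runs to month 12. Discontinuing intervention therefore has some meaning after the procedure, and 7.1 keeps such a person in. This stands, but it does not clearly cover someone formally withdrawn under 7.2.

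**Some weights cannot be had or are hard to use.** Death yields none. People removed for missing visits are the least likely to attend. After surgery or another weight-loss therapy, the month-12 weight partly reflects that treatment, and whether to use it is partly a choice of estimand. This stands, and it makes the recoverable group smaller.

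**The effect is small and assumed.** In the 5 kg case the shift is about 0.17 of a standard error (0.370/2.160). A net imbalance of one participant at 5 kg shifts the difference by only 0.19 kg. The extreme case above needs up to 5 of 27 removed (18.5%), all from BAE, which exceeds the 13.9% bound. Section 7.1 also halts the study for evaluation after one listed serious event, so complication removals should be few. All of this stands.

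**Handling already exists.** The board decides whether the rules apply, 20% dropout is allowed for, and multiple imputation and a sensitivity analysis for informative missingness are planned (Protocol 9.4.2, SAP 6.0). These show how far the conclusion depends on the missing weights; they do not supply weights that could have been observed.

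**The adverse-event part is weak.** It is a matter of wording, and it is the lesser part of the point.

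**Conclusion.** The concern holds and should be fixed. The protocol removes treated participants from the study and then makes no attempt to obtain their primary-endpoint weight, and the planned imputation ignores both the exit weight and the reason for leaving. The likely effect is modest: shifts of roughly 0.2 to 0.6 kg against a planned 4.7 kg, and power at 21 per arm between about 0.73 and 0.87 in place of 0.81. It is zero if removals and gaps balance. These figures rest on an assumed 3 v 1 removal, gaps of 3 to 8 kg and otherwise non-informative dropout; the direction is unknown. Confidence in the size is therefore limited, while the gap in the text is plain. What justifies acting despite the modest size is that the change is cheap and a month-12 weight not taken cannot be recovered later.

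**What to change.** Amend 7.2 so that the listed conditions and discretionary reasons trigger board or investigator review and clinical care, but do not end data collection. Unless consent is withdrawn, ask every randomised and treated participant for a scale weight in the 12-month window (±14 days, Protocol 1.3) and make an adverse-event enquiry through month 12, by telephone where needed, as 8.2.18 already allows. State in 8.3.3 that adverse-event collection runs to month 12 for these participants. Leave pregnancy as now written. Record the start date of any other weight-loss therapy, because a later weight will partly reflect it.

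The cost is protocol and consent wording plus a few visits that are already scheduled; participants live or work within 65 miles (Protocol 5.1). Some will decline, so not every weight will be recovered.

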Sucralfate is used to treat and prevent duodenal ulcers, as well as other conditions as determined by a doctor. Sucralfate works by forming a “barrier” or “coating” over the ulcer, protecting the ulcer from stomach acid and allowing it to heal. Sucralfate contains an aluminum salt. The most common side effects seen are constipation (2-3%) and bezoar formation. Less commonly reported effects include flatulence, headache, hypophosphatemia, and dry mouth.

Omeprazole and sucralfate will be prescribed to every participant. Antibiotics will only be prescribed to treat an accompanying infection.

Pain Management

IV acetaminophen (or a similar pain management medication) will be given prophylactically for pain during and after the procedure. Dosage of IV acetaminophen will follow standard of care guidelines for use and will be paid for by the study. The most common adverse event associated with IV acetaminophen are nausea, vomiting, headache, and insomnia.

CT Angiography

Allergy to the contrast agent or injury from radiation exposure during imaging are possible. If a participant has an allergic reaction to the contrast agent, he/she will not be allowed to continue with the embolization procedure.

Radiation Exposure

This research study includes exposure to radiation from x-rays or gamma-rays (CT scan, gastric-emptying study, bariatric embolization). This radiation exposure is for research purposes only, and is not part of the participants' medical care. X-rays and gamma rays can damage the genetic material (DNA) in cells. At low doses, cells usually can repair this damage.

The radiation exposure that participants will receive is an average of 4.2 rem, depending on the participants' diabetic status, weight, and procedural difficulty. This exposure is more than the 0.3 rem that the average person in the US gets each year from natural sources like the sun, outer space, air, food, and soil. Most participants will receive less than the 5 rem of radiation that is allowed each year for people who are exposed to radiation in their jobs.

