6 STUDY INTERVENTION

6.1 STUDY INTERVENTION(S) ADMINISTRATION

6.1.1 STUDY INTERVENTION DESCRIPTION

This study is being conducted under IDE G190208 utilizing an investigational device, BTG-001933, which is a radiopaque embolic bead 100-200 µm (Biocompatibles UK, Ltd) intended to be used for bariatric embolization [of the left gastric and/or gastroepiploic arteries](#). The summary of test validation studies is on file with the FDA and available in the Investigator's Brochure.

Control Arm Procedures

Participants randomized to the control arm will follow the same screening and pre-procedure assessment, and will also take the same pre-procedure medications. After becoming eligible, participants will be scheduled for their procedure. On procedure day, the interventional radiologist will determine radial or groin access in the post-anesthesia care unit per local policy. After the participant and procedure area are prepped, and a basic tray is opened, all participants will be given standard moderate sedation medications. At this point, the participant will have a drape placed over a drape support above their face to limit their vision and be given ear plugs and noise-cancelling headphones to dampen their hearing, preventing them from seeing and hearing the procedure but still allowing them to keep in contact with the procedure team. The participant will be randomized to either the control or intervention arm using central randomization software. Participants randomized to the control arm will receive no other procedural intervention. The procedural team instead will follow a prescribed simulated protocol that will mimic an actual embolization procedure. All participants will receive subcutaneous lidocaine and a skin nick to their groin or their wrist as pre-determined by the operating physician in the pre-anesthesia care unit, including those randomized to the control arm. If the skin nick is on the wrist, the operating physician will close it with an external compression device, and if it is in the groin, the physician will hold pressure for at least 5 minutes.

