9.2 SAMPLE SIZE DETERMINATION

Sample sizes per randomized treatment arm for the proposed study are based on providing sufficient power for testing the primary hypothesis that BAE leads to larger mean weight loss from baseline than a sham procedure.

Based on previous data, it is anticipated that the mean weight loss from baseline at 12-months post-randomization in the BAE arm will be at least 8 kg.(21, 36, 37) In contrast, we expect that participants in the sham arm will lose 3.3 kg at 12 months (corresponding to 3% weight loss from a baseline weight of 110 kg). Also, a common standard deviation for the change in weight from baseline at 12 months of 7 kg is assumed based on the data from the prior BEAT Obesity trial. Using a two-sample t-test and a two-sided alpha of 0.2, 21 participants in each arm will provide 80% power. The sample size is increased to 27 participants in each arm (i.e. a total of 54 randomized participants) to take account of an expected 20% drop-out rate by the time of the 12-month assessment. Since this is a phase 2 study, it is appropriate to use a two-sided alpha greater than the standard 0.05 value.

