9.3 POPULATIONS FOR ANALYSES

Statistical analyses will follow the intent-to-treat paradigm, meaning all participants will be analyzed according to the treatment group to which they were randomized. However, we will also perform an analysis according to a modified intention-to-treat (mITT) paradigm. As defined here, mITT means that all participants will be analyzed based on the treatment arm to which they were randomized, provided that they had exposure to the treatment protocol in their assigned arm. Participants who are randomized to a particular treatment arm, but who do not receive exposure to this treatment will be considered as 'mis-randomized', and will not be included in the mITT population. Reasons for participant mis-randomization include: 1) discovering post-randomization that a given participant does not meet the inclusion / exclusion criteria and is subsequently withdrawn from the study, 2) a participant refuses treatment after randomization, 3) a clinical investigator refuses to treat a participant post-randomization according to the protocol for the treatment arm to which the participant was assigned for any reason, and 4) the participant withdraws from the study post-randomization, but prior to receiving exposure to study treatment, for any reason.

The ten pilot participants recruited in the proposed trial will not be analyzed with the participants recruited through randomization. Rather, these ten pilot participants will be used to test and refine the trial protocol, and data collection procedures.

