3.2 Randomization

If all eligibility criteria for the study have been met by a given patient, and the patient consents to participate in the study, then this patient will be randomized into one of the two treatment groups via a computer-generated randomization scheme. Additionally, stratified randomization by diabetic status will be utilized to remove its potential confounding effect in comparing weight loss between treatment arms. Upon randomization/enrollment, each patient will be assigned a unique numeric patient identity code. Once randomized, the patient will be scheduled for their assigned procedure, and will follow the steps of the procedure as outlined in the clinical protocol.

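### Participants randomised but not treated may be replaced, and the SAP's efficacy set also omits them; together the two rules allow exclusion and substitution with the arm known

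*Protocol*

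**What the plan says.** **Replacement.** Protocol 7.2: "Subjects who sign the informed consent form and are randomized but do not receive the study intervention may be replaced". By contrast, participants who were treated and later leave or "are withdrawn or discontinued from the study will not be replaced". The section names no decision-maker for replacement and no permitted reasons. It does not say which allocation the replacement takes, or what happens to the data of the person replaced.

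**Timing and knowledge of the arm.** Protocol 6.1.1 schedules the procedure first and randomises on the day, after sedation, draping and hearing protection: "The participant will be randomized to either the control or intervention arm using central randomization software". The schedule in protocol 1.3 also puts randomisation on procedure day. Protocol 6.3 states: "Unblinded members of the study team will perform the procedure and have access to the medical record in case of emergency". SAP 3.3 accepts that the surgical team cannot be blinded. SAP 3.2 gives the opposite order: "Once randomized, the patient will be scheduled for their assigned procedure".

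**Analysis sets.** Protocol 9.3 promises intention-to-treat and adds a modified set without participants who were not exposed to their assigned treatment. One listed reason for non-exposure is that "a clinical investigator refuses to treat a participant post-randomization" under the assigned protocol, for any reason. SAP 4.1 restricts the efficacy set to those who underwent and completed the assigned procedure and have at least one later outcome. SAP 1.0 gives the SAP precedence over the protocol's analysis plan, with major changes to the primary analysis also to appear in a protocol amendment.

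**Sample size.** Protocol 9.2 raises 21 per arm to 27 "to take account of an expected 20% drop-out rate by the time of the 12-month assessment".

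**The concern.** Under the protocol's sequence, anyone who is randomised but not treated is lost after the people in the room know the arm. The two procedures then ask very different things. Sham needs lidocaine, a skin nick and a simulation. BAE needs arterial access, selection of the target vessels, advancement of a microcatheter and infusion to stasis (protocol 6.1.1). It is reasonable to expect non-receipt to fall more often in the BAE arm, although no document counts it.

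The two rules act together. The Full Analysis Set takes the untreated participant out of the efficacy comparison, and protocol 7.2 allows someone else to be brought in. The first step can bias the comparison. The second restores the headcount, so the loss no longer shows in the sample size. What is at stake is the comparability that randomising in the procedure room is meant to secure, in a trial that tests at a two-sided level of 0.20.

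The wording adds a smaller difficulty. The synopsis describes the study intervention as embolization only, so protocol 7.2 does not say clearly what non-receipt means in the sham arm.

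**Working it through.** **Inputs.** From protocol 9.2 and SAP 3.8: mean loss 8 kg (BAE) and 3.3 kg (sham), so δ = 4.7 kg; SD 7 kg; two-sided alpha 0.20; power 80%; 21 per arm raised to 27 for 20% drop-out. The number untreated in the BAE arm, *k*, is not given anywhere. I take *k* = 1 to 3, which is 3.7% to 11.1% of 27, with none untreated in sham. Both are assumptions.

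**1. The plan's own figure.** Normal approximation: n = 2 × [7 × (1.2816 + 0.8416) / 4.7]² = 19.999, so 20 per arm. Exact t-test power is 0.794 at 20 and 0.809 at 21, so 21 is right. Drop-out: 21 / 0.8 = 26.25, so 27. The stated sample size reproduces, with a margin of 27 − 21 = 6 per arm. With 27 × 0.8 = 21.6 evaluable per arm, power is 0.817.

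**2. Power without replacement.** Two cases, each with the full 20% drop-out:

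- *Excluded:* the *k* untreated BAE participants leave the analysis, so BAE has (27 − k) × 0.8 evaluable against 21.6 in sham.
- *Kept:* all stay as randomised, with 21.6 evaluable per arm and untreated BAE participants assumed to have the sham mean, so δ becomes 4.7 × (27 − k) / 27.

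| k | Excluded: BAE n | Power | Kept: δ (kg) | Power |
|---|---|---|---|---|
| 0 | 21.6 | 0.817 | 4.70 | 0.817 |
| 1 | 20.8 | 0.811 | 4.53 | 0.795 |
| 2 | 20.0 | 0.805 | 4.35 | 0.771 |
| 3 | 19.2 | 0.799 | 4.18 | 0.746 |

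If untreated participants are excluded, replacement is hardly needed for power. If they are kept, power falls through dilution. Replacement does not remove that dilution as long as the replaced participants stay in the analysis.

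**3. Possible bias.** Suppose *k* of 27 BAE participants are dropped and would have lost *g* kg less than the rest. The mean of those left exceeds the mean of all 27 by k × g / 27. Replacements who resemble the rest leave that shift unchanged.

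- For *k* = 1 to 5 and *g* = 2 to 7 kg (assumed), the shift runs from 1 × 2 / 27 = 0.07 kg to 5 × 7 / 27 = 1.30 kg.
- For *k* = 3 and *g* = 4 kg, it is 12 / 27 = 0.44 kg, or 9% of 4.7 kg.
- With SE = 7 × √(2/21) = 2.16 kg and no true effect, the tail favouring BAE is then P(Z > 1.2816 − 0.44/2.16) = 0.141 instead of 0.10. The two-sided error is 0.2095 instead of 0.20.

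**4. Order of events.** Protocol 1.3 and 6.1.1: schedule, then randomise on procedure day. SAP 3.2: randomise, then schedule. Both cannot be followed. The SAP order leaves an interval after allocation in which either arm could lose participants.

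**The case against.** Much can be said for the plan, and several stronger readings fail.

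- **That non-receipt does arise mainly in the BAE arm.** No count, rate or arm is given. Vascular anatomy is checked by CT angiography before allocation (protocol 5.1), and known contrast allergy is an exclusion (5.2). The sentence that a participant who reacts to contrast "he/she will not be allowed to continue with the embolization procedure" sits in the paragraph on CT angiography and most naturally concerns that screening scan. Only the weaker statement stands: it could fall mainly there.
- **That replacement breaks intention-to-treat.** By itself it removes nobody. The exclusion comes from SAP 4.1.
- **That the unblinded team swaps a hard BAE case for an easy one.** Protocol 7.2 does not say who decides, nor that the replacement enters the same arm. If the replacement takes the next allocation, there is no same-arm swap. The exclusion under SAP 4.1 remains either way.
- **That every failed embolization is replaceable.** SAP 4.2 treats a partial embolization as having undergone the procedure, so an abandoned case may not count as non-receipt under 7.2. It would still fall outside the Full Analysis Set, which requires completion.
- **That replaced participants are lost to follow-up.** Protocol 7.1 says stopping the intervention is not leaving the study, and 6.1.1 and 6.3 put all participants on the same follow-up schedule. Only two of the four reasons in 9.3 mention withdrawal. It stays unclear whether these passages cover someone never treated.
- **That the 20% allowance already covers this.** It is stated for drop-out by month 12. With 10% untreated as well, 27 × 0.9 × 0.8 = 19.4 treated and evaluable BAE participants remain, below 21.
- **That SAP 3.2 discloses allocations to scheduling staff.** This is speculation, and SAP 3.2 itself defers to the protocol for the procedure steps. The contradiction in order is real all the same.

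**Conclusion.** The point holds as a gap in the rules, not as a demonstrated bias. Protocol 7.2 leaves replacement discretionary and unspecified, allocation is known in the room, 9.3 accepts refusal to treat for any reason, and SAP 4.1 drops those who did not complete the procedure. Followed as written, the plan allows arm-aware exclusion and substitution in the efficacy analysis.

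The size cannot be fixed from the documents. Over the assumed grid the shift in the BAE mean is 0.07 to 1.30 kg, with the upper end needing both many untreated participants and a large difference between them and the rest. Keeping everyone as randomised costs power: down to about 0.75 with three untreated BAE participants and the full 20% drop-out, if their mean equals that of sham. A cheap improvement, worth making before data lock.

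**What to change.** 1. **Protocol 7.2.** State that no participant is replaced after randomisation. A participant who is randomised but does not receive the assigned procedure keeps the allocated arm and is weighed and assessed for adverse events to month 12, unless consent is withdrawn. Refer to the assigned procedure, so that the rule reads the same way in both arms.
2. **SAP 4.1.** Define the primary efficacy set as all randomised participants, as randomised, in line with protocol 9.3. Keep the set of those who completed the procedure as a sensitivity analysis. Report untreated participants by arm with reasons; SAP 2.0 does not list them as a category of its own. Without this step the change to 7.2 has no effect on the efficacy result.
3. **SAP 3.2.** Reconcile it with protocol 1.3 and 6.1.1, so that both documents give one order of scheduling and randomisation.

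Follow-up of untreated participants matters for the analysis too. The imputation model in SAP 6.0 is built from completers within each arm, so an unmeasured untreated BAE participant would be given values predicted mostly from treated ones.

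**Cost.** A few sentences in two documents, follow-up visits for a few participants, and the loss of power shown above. If the sponsor wants 80% power under intention-to-treat, the allowance should be set for drop-out and non-receipt together before the analysis, and not made up by replacement.
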